5.1.1.3 Tumor Lysis Syndrome

Tumor lysis syndrome (TLS) is a potentially life-threatening metabolic disorder that occurs when tumor cells release their contents into the bloodstream, either spontaneously or in response to therapy, leading to characteristic findings of hyperuricemia, hyperkalemia, hyperphosphatemia, and hypocalcemia. This complication is common in patients with acute leukemia but had been very rare with idasanutlin. Please refer to the Idasanutlin Investigator's Brochure.

5.1.1.4 Infections

Infections of various etiologies have been reported in patients with AML in Study NP28679, and patients with AML generally have a higher susceptibility to infection. Infectious diarrhea, and in particular *C. difficile* infection, was reported in approximately 10% of patients with AML administered idasanutlin in Study NP28679, including 1 fatal

case of *C. difficile* infection. In addition to institutional guidelines, specific instructions for the management of *C. difficile* infection are provided in [Appendix 5](#).

5.1.1.5 Electrolyte Disorders

Hypokalemia, hypophosphatemia, and hypomagnesemia were commonly observed in patients treated with idasanutlin. In addition to institutional guidelines, electrolytes should be monitored during treatment, and electrolyte disorders should be treated according to institutional guidelines.

5.1.1.6 Other Adverse Events

Other adverse events commonly reported with idasanutlin include fatigue, asthenia, pyrexia, peripheral edema, headache, dyspnea, dizziness, and chills. These adverse events have been of mild severity and controllable with symptomatic treatment and/or nutritional support.

All enrolled patients will be evaluated clinically and with standard laboratory tests before and at regular intervals during their participation in this study. Safety evaluations will consist of medical interviews, recording of adverse events, physical examinations, ECGs as clinically indicated, vital signs, and laboratory measurements (hematology, chemistry, and urinalysis).

5.1.2 Risk of Overlapping Toxicities

Overlapping toxicities from the combined administration of cytarabine, daunorubicin and idasanutlin are anticipated during study treatment phase. These toxicities include myelosuppression (thrombocytopenia, neutropenia, and febrile neutropenia), infectious complications, and GI disorders (diarrhea, nausea and vomiting; see [Table 7](#)).

Table 7 Overlapping Toxicities Grade \geq 3: Idasanutlin, Cytarabine, and Daunorubicin

| Adverse Events | | 7+3 ^a | Idasanutlin ^b |
|------------------------|---------------------------------|------------------------------------|--------------------------|
| Hematologic toxicities | Thrombocytopenia | 98% | 24.5% |
| | Neutropenia/febrile neutropenia | 91%/35% | 12.4%/26% |
| | Anemia | 76% | 18.2% |
| Infections | Infections (SOC) | 49%–73.7% (<60 yr) 86% (>60 yr) | 30.2% |
| GI toxicities | Diarrhea | 10.8% | 13% |
| | Nausea/vomiting | | 4%/1.3% |

7 + 3 = 7 days of cytarabine plus 3 days of daunorubicin; AML=acute myeloid leukemia; GI=gastrointestinal; R/R=relapsed or refractory; SOC=system organ class.

^a Fernandez et al. 2009; Löwenberg et al. 2009; Lee 2011.

^b Idasanutlin Investigator’s Brochure, Version 10. Cumulative incidences across all solid tumor and R/R AML studies (except GH29914).

5.1.3 Management of Patients Who Experience Specific Adverse Events

Patients should be assessed clinically before each study treatment administration.

Guidelines for management of toxicities (see [Appendix 5](#)) are based on laboratory values obtained within 3 days prior to Day 1 of each scheduled drug administration. Dosing will occur only if a patient’s clinical assessment and laboratory test values are acceptable.

Treatment delays apply to all toxicities described below; dose modifications apply only to toxicities that are considered to be related to idasanutlin. The dose of idasanutlin may be reduced as outlined in [Table 8](#).

Table 8 Idasanutlin Dose-Reduction Steps

| Initial Dose | Dose Reduction in Milligrams | | |
|--------------|------------------------------|-----------------------------------|-----------------------------------|
| | Step 1 | Step 2 | Step 3 |
| 150 mg | Minus 50 mg | No further reduction ^a | No further reduction ^a |
| 200 mg | Minus 50 mg | Minus 50 mg | No further reduction ^a |
| 250 mg | Minus 100 mg | Minus 50 mg | No further reduction ^a |
| 300 mg | Minus 100 mg | Minus 50 mg | Minus 50 mg |
| 350 mg | Minus 100 mg | Minus 100 mg | Minus 50 mg |
| 400 mg | Minus 100 mg | Minus 100 mg | Minus 50 mg |

^a When no further idasanutlin dose reduction is possible, the patient will be discontinued from the study drug.

Toxicities that occur during the cycle and subside prior to the next cycle should not trigger the suggested dose modifications. Guidelines for management of toxicities during treatment are provided in Sections 5.1.3.1 and 5.1.3.2. Exceptions to those guidelines may be allowed by the Sponsor after careful review of the case and discussion with the Medical Monitor.

5.1.3.1 Toxicities during Induction and Consolidation Treatment Hematologic Toxicities

Table 9 provides guidelines for management of hematologic toxicities that occur during induction and consolidation treatments. Hematologic toxicity is defined as neutropenia, febrile neutropenia, anemia, or thrombocytopenia. If toxicity is thought to be caused mainly by AML, the investigator may decide not to reduce idasanutlin dose.

Table 9 Guidelines for Management of Idasanutlin-Related Hematologic Toxicities in Induction and Consolidation Treatment

| Event | Action to Be Taken |
|-----------------------------------|--|
| Grade 3 or 4 hematologic toxicity | 
For patients who have had one or no prior dose reductions:
 
 • Withhold study treatment. • Administer RBCs or platelets as required. • If patient has not already initiated G-CSF, initiate prophylactic G-CSF for current and subsequent cycles (consolidation only) as required. • If improvement to Grade ≤ 2 or baseline within ≤ 21 days after the scheduled date for the next cycle, resume idasanutlin at current dose (consolidation only). • If improvement to Grade ≤ 2 or baseline 21–28 days after the scheduled date for the next cycle, resume idasanutlin at a reduced dose according to guidelines for current and subsequent cycles (consolidation only). • No more than two dose reductions of idasanutlin are allowed per study phases (induction, consolidation) • If study treatment is withheld for >28 days, permanently discontinue study treatment. • Permanently discontinue study treatment if any of the following events occur: 
 • Grade 3 or 4 thrombocytopenia of any duration if associated with Grade ≥ 3 bleeding • Recurrent Grade 3 or 4 neutropenia if associated with fever of $> 38^{\circ}\text{C}$ for > 5 days or a documented infection despite use of G-CSF and after one idasanutlin dose reduction • Recurrent Grade 4 neutropenia or thrombocytopenia lasting more than 7 days despite use of G-CSF (for neutropenia) and after one idasanutlin dose reduction 
For patients who present with recurrent Grade 3 thrombocytopenia/neutropenia in consecutive cycles:
 
 • If despite the use of G-CSF, for subsequent cycles, reduce idasanutlin to the next dose level. 
For patients who have had two dose reductions in the same study phase (induction, consolidation) or for patients who reach the lowest dose level and no further dose reduction is applicable.
 
 • Permanently discontinue study treatment |

G-CSF = granulocyte colony-stimulating factor.

5.1.3.1.1 Non-Hematologic Toxicities

Guidelines for management of non-hematologic toxicities that occur during induction and consolidation treatment are presented in [Table 10](#) and [Table 11](#).

Table 10 Guidelines for Management of Idasanutlin-Related Gastrointestinal Toxicities in Induction and Consolidation

| Event | Action to Be Taken |
|----------|--|
| Diarrhea | 
Permanently discontinue study treatment for Grade 4 events.
 
Grade 3 diarrhea:
 
• If Grade 3 diarrhea occurs between Days 1 and 5 of the treatment cycle, withhold idasanutlin only if diarrhea does not improve to Grade ≤ 2 within 72 hours with appropriate treatment. After the study treatment is withheld, if diarrhea improves to Grade ≤ 2, resume idasanutlin at a reduced dose according to guidelines in Sections 5.1.3 for current and subsequent cycles. |
| Vomiting | 
Grade 4 vomiting:
 
• Permanently discontinue study treatment. 
Grade 1, 2, or 3 vomiting:
 
• If vomiting occurs within 15 minutes of taking idasanutlin, and all expelled tablets are still intact, another dose may be given and the second dose noted in the drug log. Otherwise, no replacement dose is to be given (see Section 4.3.2). |

Table 11 Guidelines for Management of Idasanutlin-Related Non-Hematologic Toxicities in Induction and Consolidation

| Event | Action to Be Taken |
|--|---|
| 
 General guidance for treatment delays, discontinuation, and resumption | 
 If study treatment is withheld for >21 days because of a toxicity that is attributable to study treatment, permanently discontinue study treatment. Permanently discontinue study treatment for Grade 4 events. Dosing may be resumed after resolution to Grade ≤ 2 or baseline status. Resumption of dosing without complete resolution of toxicity may be considered in special circumstances after having obtained Medical Monitor agreement. |
| IRRs and anaphylaxis | 
 Guidelines for the management of IRRs are provided in Appendix 5. In case of Grade 4 IRRs or anaphylaxis, study treatment should be permanently discontinued. |

5.1.3.2 Toxicities during Maintenance Treatment

Guidelines for management of toxicities that occur during maintenance treatment are presented in [Table 12](#).

Table 12 Guidelines for Management of Toxicities That Occur during Maintenance

| Event | Action to Be Taken |
|---|--|
| Hematologic toxicity: Grade 3 or 4 | 
• Withhold study treatment.• If improvement to Grade ≤ 2 within 14 days, resume treatment at full dose.• If improvement to Grade ≤ 2 after >14 days, resume study drug at next lower dose for subsequent cycles per guideline in Section 5.1.3. Patients who are not eligible for further dose reductions should be permanently discontinued.• Patients missing two consecutive cycles should be permanently discontinued. |
| Non-hematologic toxicity: Grade ≥ 3 | 
• Withhold study treatment.• If improvement to Grade ≤ 2 within 14 days, resume treatment at full dose.• If improvement to Grade ≤ 2 after >14 days, resume study drug at next lower dose for subsequent cycles per guideline in Section 5.1.3. Patients who are not eligible for further dose reductions should be permanently discontinued.• Patients missing two consecutive cycles should be permanently discontinued. |

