3.3 RATIONALE FOR STUDY DESIGN

3.3.1 Rationale for Idasanutlin Dose and Schedule

Idasanutlin dosing for this study is based on experience in both single-agent testing (Studies NP27872 and NP28902) in solid tumors and from the combination with 1 g/m² cytarabine in Study NP28679 in patients with both R/R and elderly front-line AML. The lowest dose where responses were seen in AML was 200 mg adjusted for formulation differences in combination with cytarabine 1 g/m², and as this dose has been proven safe and allowed for escalation (see the Idasanutlin Investigator's Brochure), it has been chosen as the starting dose for idasanutlin. A lower dose of 150 mg has been chosen in maintenance to minimize side effects as patients in remission would not require aggressive treatment. This dose is below the MTD in solid tumor (see the Idasanutlin Investigator's Brochure) where patients have functional bone marrow and is used in polycythemia vera studies over multiple cycles (see the Idasanutlin Investigator's Brochure).

The QD×5-day schedule was proven safe and efficacious in the Phase I AML study NP28679 and is investigated in the ongoing registrational R/R AML study (WO29519). Therefore, it was chosen also for the front-line regimen.

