4.3.2.4 Premedication

Patient must receive premedication as outlined in [Table 6](#). Further details are provided in [Appendix 5](#).

Table 6 Premedication

| Timepoints | Premedication | Administration |
|---|--|--|
| Induction and consolidation All cycles | Anti-emetic medicines (second-generation anti-emetic medicines, such as palonosetron, ondansetron, or granisetron) | Mandatory prior to each idasanutlin dosing Dosing as per individual drug prescribing information |
| | Anti-diarrheal medicines (unless medically contraindicated) ^a | Mandatory prior to each idasanutlin dosing. Dosing as per individual drug prescribing information |
| | Anti-fungal agents | Strongly recommended prior Day 1 of Cycle 1 Dosing as per individual drug prescribing information (until neutrophil count recovery Grade ≤ 2) |
| | Antimicrobial medicines | Strongly recommended prior Day 1 of Cycle 1 Dosing as per individual drug prescribing information (until neutrophil count recovery Grade ≤ 2) |
| Maintenance All cycles | Prophylaxis may be utilized on the basis of investigator discretion and patient tolerability. Supportive therapies, including prophylaxis for diarrhea and nausea, are encouraged in the maintenance phase of the study | |

^a Contraindication should be recorded in the medical history or as a separate adverse event.

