5.1.1.1 Gastrointestinal Toxicity

The adverse GI events in the Phase I idasanutlin studies include primarily diarrhea, nausea, vomiting, abdominal pain, constipation, and anorexia. Diarrhea was the most common adverse event observed in >90% of patients in the AML study NP28679 (mostly Grades 1 and 2 in severity). Nausea and vomiting were also reported in this study but to a lesser extent and all events were generally Grades 1 and 2. Supportive therapies, including prophylaxis for diarrhea and nausea, are encouraged in this study. In addition to institutional guidelines, specific instructions for the management of GI side effects are provided in Section [5.1.3.1](#) and [Appendix 5](#).

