Appendix 5 Toxicity Management Guidelines

DIARRHEA MANAGEMENT GUIDELINES AND RECOMMENDATIONS

Diarrhea has been the most frequently reported adverse event in patients with acute myeloid leukemia (AML) administered with idasanutlin (Study NP28679).

Prior to first study medication administration

Patients should be carefully screened for active GI conditions (e.g., graft-versus-host disease, $G \geq 2$) and uncontrolled irritable bowel disease (i.e., Crohn's disease, ulcerative colitis, diverticulosis-associated colitis, and Behçet disease) prior to enrollment. Patients with active GI conditions as noted in the exclusion criteria are not permitted to start treatment.

Establish the individual patient's normal bowel function. Discuss how function could change in the future with treatment. Discuss dietary management/rehydration.

Prophylactic antidiarrheal therapy is to be instituted for all patients administered study medications in induction and consolidation as follows (unless medically contra-indicated):

Loading dose of loperamide 4 mg orally 30 minutes before first administration of idasanutlin

Instruct patients on warning signs (e.g., bloody stools, associated fever, and dizziness).

- **Event management**

Should diarrhea occur: administer loperamide 2 mg orally every 4 hours or after every unformed stool to a maximum dose of 16 mg/24 hr.

Rule out other or concomitant causes, including medications (e.g., stool softeners, laxatives, and antacids), *C. difficile* infection (CDI), malabsorption/lactose intolerance, fecal impaction, and dietary supplements high in fiber

Dietary measures: Discontinue all lactose-containing products, alcohol and high-osmolar supplements; instruct patients to eat frequent small meals (e.g., bananas, rice, apples, and toast).

Loperamide treatment should be continued until patient is diarrhea-free for ≥ 24 hours or until Day 10 of the specific cycle, whichever occurs first.

Record the number of stools and report complications (e.g., fever or dizziness upon standing).

Encourage adequate hydration.

Monitor electrolytes daily (i.e., potassium, magnesium, calcium, and sodium).

Administer IV fluids as clinically indicated and aim at all times for electrolyte correction.

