Appendix 5: Toxicity Management Guidelines (cont.)

Table 1 Diarrhea Management According to CTCAE Grade

| Diarrhea Grade | Recommended Actions |
|----------------|---|
| Grade 1/2 | 
a) See all supportive recommendations indicated above (i.e., loperamide, symptomatic management, dietary counselling, rehydration, and electrolyte correction).b) No change in study medication dose will be implemented for Grade ≤ 2 diarrhea; patients should receive maximal supportive care as described above.c) If diarrhea persists after 48 – 72 hours despite administration of the maximum recommended daily loperamide dose (16 mg/24 hr), second-line agents may be considered. |
| Grade 3 | 
d) Consider second-line agents (i.e., diphenoxylate, atropine, octreotide, budesonide, or tincture of opium) if the patient is receiving loperamide at the maximum recommended daily dose (16 mg/24 hr).e) If no improvement is observed within 24 hours, test for CDI.f) If, despite adequate supportive care, Grade 3 diarrhea persists >48 hours without responding to loperamide at the maximum recommended daily dose (16 mg/24 hr), the idasanutlin dose should be reduced as per Table 11.g) If clinical characteristics have NOT improved to Grade ≤ 1 or baseline by 28 days despite the patient receiving maximal supportive care, idasanutlin must be permanently discontinued.h) If the diarrhea recurs at Grade 3 despite supportive care and idasanutlin dose reduction, idasanutlin must be permanently discontinued. |
| Grade 4 | 
i) If, despite prophylaxis and adequate supportive care, Grade 4 diarrhea is diagnosed, idasanutlin must be permanently discontinued.j) Consider second-line agents (i.e., diphenoxylate, atropine, octreotide, budesonide, or tincture of opium) if the patient is currently receiving loperamide at the maximum recommended daily dose (16 mg/24 hr).k) If no improvement is observed within 24 hours, test for CDI. |

CDI = *Clostridium difficile* infection; CTCAE = Common Terminology Criteria for Adverse Events.

CLOSTRIDIUM DIFFICILE INFECTION

Due to the high incidence of diarrhea, CDI may occur undetected. Once diagnosed, monitoring CDI is also challenging, as treatment-induced diarrhea may be persistent. The risk factors for CDI are common in this patient population (treatment with systemic

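### Grade 4 diarrhea in maintenance: Table 12 lets idasanutlin restart at full dose, while Appendix 5 requires a permanent stop, and no text says which governs

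*Combined protocol and SAP*

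**What the plan says.** Section 5.1.3.2, Table 12, covers maintenance. Its non-hematologic row takes in every event of Grade 3 or higher, with no separate line for Grade 4 or for diarrhea. Study treatment is withheld. If the event improves to Grade 2 or better "within 14 days, resume treatment at full dose". If improvement takes longer, dosing resumes at the next lower level. A permanent stop follows only when no reduction step is left or two consecutive cycles are missed.

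Appendix 5, Table 1, Grade 4, item i: "If, despite prophylaxis and adequate supportive care, Grade 4 diarrhea is diagnosed, idasanutlin must be permanently discontinued".

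Section 5.1.3.1.1, Table 10, which covers induction and consolidation, says under diarrhea: "Permanently discontinue study treatment for Grade 4 events".

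On prophylaxis, Appendix 5 says: "Prophylactic antidiarrheal therapy is to be instituted for all patients administered study medications in induction and consolidation as follows". For maintenance, Table 6 (Section 4.3.2.4) leaves prophylaxis to investigator discretion and adds: "Supportive therapies, including prophylaxis for diarrhea and nausea, are encouraged in the maintenance phase of the study".

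Section 5.1.3 adds a general rule: "Toxicities that occur during the cycle and subside prior to the next cycle should not trigger the suggested dose modifications".

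**The concern.** Idasanutlin is the only study drug in maintenance, so resuming it and stopping it for good are opposite instructions for the same event. Two sites reading the same protocol could act differently and both claim compliance. Maintenance exposure and discontinuation counts would then mix two rules.

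The maintenance rule is also the laxer one. Under Table 10, even Grade 3 diarrhea that leads to withholding restarts at a reduced dose; under Table 12, Grade 4 diarrhea can restart at full dose. Table 12 has no recurrence rule either. Grade 4 diarrhea in successive cycles, each time recovering within 14 days, would never trigger a reduction or a stop. The general rule in Section 5.1.3 about toxicities that subside before the next cycle points the same way.

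No reason is given for the difference, and the stated thinking on maintenance leans the other way: "A lower dose of 150 mg has been chosen in maintenance to minimize side effects as patients in remission would not require aggressive treatment". At stake is re-exposure after a Grade 4 event, in a phase for which Section 1.1 acknowledges that benefit has not been conclusively shown.

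**Working it through.** The plan states no figure to reproduce. The check is a comparison of texts, followed by a count of doses per event.

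**1. The rules side by side, for Grade 4 diarrhea**

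| Source | Phase covered | Action |
|---|---|---|
| Table 10 | Induction, consolidation | Permanent stop |
| Appendix 5 Table 1, item i | None named | Permanent stop of idasanutlin, if the event occurs despite prophylaxis and support |
| Table 12 | Maintenance | Withhold; full dose if Grade 2 or better within 14 days, next lower dose if later |

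In induction and consolidation, Table 10 and Appendix 5 agree that idasanutlin stops. In maintenance, Table 12 and Appendix 5 do not agree.

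**2. Does Appendix 5 reach maintenance?** Sections 5.1.1 and 5.1.3 both invoke it without a phase limit, and Section 5.1.3 is the parent of the section holding Table 12. Appendix 5 names phases where it wants to: the mandatory antidiarrheal and antiemetic prophylaxis is tied to induction and consolidation. The diarrhea grade table carries no such limit. Nothing in Sections 4.6.1, 5.1.1.1 or 5.1.3 ranks Table 12 against Appendix 5.

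**3. Which maintenance patients are affected?**
- Prophylaxis given: item i's condition is met once support has also been adequate. Table 12 says restart, item i says stop, and both cannot be followed.
- No prophylaxis given: a site can argue that item i's condition is not met and that Table 12 alone applies. Another site can read item i as a general Grade 4 rule. The text does not settle it.

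**4. Size per event**

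Inputs: 12 maintenance cycles of 28 days, dosing on Days 1–5, 150 mg per dose (Tables 4 and 5; Appendix 1); one reduction step of 50 mg from 150 mg, and no further step (Table 8).

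- Planned maintenance: 12 × 5 = 60 doses; 60 × 150 = 9,000 mg.
- Doses left after a Day 5 event in Cycle k: (12 − k) × 5.
- Recovery limit for full dose: Day 5 + 14 = Day 19, before the next cycle opens on Day 29. The patient misses no dose.

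| Case | Table 12 | Item i |
|---|---|---|
| Cycle 1, recovery by Day 19 | (12 − 1) × 5 = 55 doses; 55 × 150 = 8,250 mg | 0 |
| Cycle 1, recovery after 14 days but before Day 29 | up to 55 doses at 150 − 50 = 100 mg; 5,500 mg | 0 |
| Cycle 6, recovery by Day 19 | (12 − 6) × 5 = 30 doses; 30 × 150 = 4,500 mg | 0 |

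These are maxima within the 12 planned cycles. They assume no recurrence that leads to a stop, no relapse and no other discontinuation. Tables 4 and 5 allow escalation to 200 mg in maintenance, so full dose could be higher than 150 mg.

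**The case against.** **Appendix 5 may have been written for induction and consolidation.** Item f of the same table sends dose reduction to Table 11, an induction and consolidation table. Section 5.1.1.1 says that "specific instructions for the management of GI side effects are provided in Section" 5.1.3.1 and Appendix 5, and Section 5.1.3.1 is the induction and consolidation section. These are fair signs of focus, but no sentence confines item i to those phases. If it were so confined, a phase-specific rule would remain: single-agent idasanutlin at 150 mg against combination chemotherapy at possibly higher doses. A sponsor may choose that, but the protocol does not say that it did.

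**Item i is conditional on prophylaxis.** This stands. A reader might infer that no site could follow both rules for any maintenance patient. The text supports that only where prophylaxis was given; elsewhere the fault is ambiguity.

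**Safeguards exist.** Section 4.6.1 makes unacceptable toxicity a mandatory stop. Section 5.1.3 requires acceptable clinical and laboratory findings before dosing and permits exceptions after Sponsor review. Section 5.2.3 requires diarrhea of Grade 2 or higher to be reported within 24 hours. These lower the risk, but none names Grade 4 diarrhea as a stop, and Table 12's written default is still to restart.

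**Size.** A reader might apply the 13% for Grade 3 or higher diarrhea in Table 7 to the 30 post-consolidation patients. The documents do not support that. The 13% pools solid-tumor and relapsed or refractory AML studies, in a program that included other doses and cytarabine combinations, and it does not separate Grade 4. Section 5.1.1.1 describes diarrhea in the AML study as mostly Grade 1 or 2.

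**Benefit and risk.** A reader might infer that Table 10 protects patients with active leukemia while Table 12 exposes patients in remission. Table 10 also governs consolidation, whose patients are already in remission, and Section 3.3.2 describes MRD-positive patients as being in greater medical need than MRD-negative ones. The case does not rest on that contrast.

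**Breadth.** A reader might infer that every Grade 4 non-hematologic event in maintenance must become a permanent stop, as Tables 10 and 11 broadly require in the earlier phases. The contradiction shown concerns diarrhea only. A wider stop could catch correctable events such as electrolyte abnormalities, and is a separate choice.

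**Conclusion.** The point holds for Grade 4 diarrhea in maintenance. Table 12 permits a restart that Appendix 5 item i forbids, and nothing ranks one over the other. The conflict is direct for maintenance patients who received prophylaxis and unresolved for those who did not. This rests on reading item i as phase-neutral, which its wording supports despite the signs of an induction and consolidation focus.

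The consequence is known per event only: up to 55 further 150 mg doses against 0 for the earliest case considered, and fewer for later cycles. No expected number of patients can be given, because the protocol reports no Grade 4 rate. The rules apply to the post-consolidation cohort and to escalation and expansion patients who reach maintenance. CR at the end of induction and the dose-finding rules are unaffected. It should be corrected because it concerns re-exposure after a Grade 4 toxicity and the correction is cheap.

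**What to change.** In Table 12, add a line stating that idasanutlin-related Grade 4 diarrhea requires permanent discontinuation of idasanutlin. In Appendix 5 Table 1, state that the Grade 4 rule applies in all phases, with or without prophylaxis. The second change removes both the scope question and the prophylaxis condition.

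The cost is two short text changes, with no new assessments and no added patients. The downside is small: lost maintenance dosing in patients who have this event.

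Two matters lie outside this fix. Extending the stop to other Grade 4 non-hematologic events is optional. The Grade 3 diarrhea rules also differ between the two places: Appendix 5 items f to h reduce the dose after 48 hours without response, require Grade 1 or baseline by 28 days, and stop on recurrence after a reduction. The sponsor could state in the same amendment whether those items apply in maintenance.
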